5.4. Photo Capture and Imaging Analysis (N=60)

• Facial Image Capture by VISIA 7 (Canfield, America)

Subjects will be asked to wear hair band, close eyes, and coordinate with image-position matching, then take pictures by trained technician. The facial photo is captured by VISIA 7 on front, left and right sides with standard, cross polarized and UV light operated by trained technician at T0 (baseline), T14d (after pre-

treatment), T15d (Timm post-procedure), T16d (1-day after self-recovery), T18d (3-day after self-recovery), T22d (7-day after self-recovery), T25d (10-day after self-recovery and product treatment start), T32d (7-day after product treatment), T39 d (14-day after product treatment).

Optical Coherence Tomography (OCT) (Michelson Diagnostics, England)

Optical Coherence Tomography (OCT) is a non-invasive imaging technique used to evaluate the retina. The image is acquired using laser light to scan the retina and results in an image that shows the retinal layers in detail. When looking at an OCT scan we see it as if the retina were cut in half and seen from the side. The Optical Coherence Tomography will be operated by trained technician at T0 (baseline), T14d (after pretreatment), T15d (Timm post-procedure), T16d (1-day after self-recovery), T18d (3-day after self-recovery), T22d (7-day after self-recovery), T25d (10-day after self-recovery and product treatment start), T32d (7-day after product treatment), T39d (14-day after product treatment).

5.5. Fractional Ultrapulse CO₂-laser

The Fractional Ultrapulse CO2-laser is a gas laser. It generates arrays which act on the dermis and promote the generation of dermal collagen and the rearrangement of collagen fibers. The instrument uses ultrapulse mode and the pulse ejects continuously or repeatedly with a frequency of 1000Hz. The Fractional Ultrapulse CO2-laser will be operated by medical technologist at T15d (Timm post-procedure).

5.6. Self-assessment Questionnaire (N=60)

- > Self-Assessment Questionnaire on product efficacy will be answered by subjects at T14d (after pretreatment), T25d (10-day after self-recovery), T32d (7-day after product treatment), T39d (14-day after product treatment) for Group 1 (N=30);
- ➤ **Self-Assessment Questionnaire on cosmeticity** will be answered by subjects at T14d (after pretreatment), T39d (after product treatment) for Group 1 (N=30).
- > Self-assessment questionnaire on post-procedure tolerance will be answered by subjects at T15d (Timm post-procedure), T16d (1-day after self-recovery), T18d (3-day after self-recovery), T22d (7-day after self-recovery), T25d (10-day after self-recovery) for all groups (N=60).

6. Product

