Investigator: Title: Dermatologist

[contact] [contact]

Test Site: China-Norm U@Test laboratory

Address: [name],

Shanghai, China

Study Objective: To evaluate the effect of a facial essence on skin barrier and skin condition after 2-week of use; And study on the repair efficacy of skin barrier and condition after receiving Fractional Ultrapulse CO₂-laser. The whole study will be divided into two dimensions to evaluate the product: the comparison of the effect before and after and the comparison with the control group.

Experimental Design:

Mono-centric, single-blind, parallel random and home use design.

Test Areas:

Whole face

Subjects:

70 female adult subjects will be enrolled and divided into 2 groups in the study, recruited according to inclusion and non-inclusion criteria listed below, and at least 60 subjects should complete the whole study (at least 30 subjects per group).

Group 1: Facial Serum Group

- Group 2: Non-treatment Group

Age: 20-50 years old

Measurements:

Clinical Assessment(N=60):

Skin qualities of skin dryness, erythema, papules, desquamation, chromatosis, edema, escharosis, elasticity, evenness, brightness, radiance, smoothness, pores on cheek, crow's feet wrinkle, epithelial confluence and overall healthy appearance will be evaluated by dermatologist at T0 (baseline), T14d (after pre-treatment), T15d (Timm post-procedure), T16d (1-day after self-recovery), T18d (3-day after self-recovery), T22d (7-day after self-recovery), T25d (10-day after self-recovery and product treatment start), T32d (7-day after product treatment), T39d (14-day after product treatment) for all groups.

Lactic Acid Stinging Test (N=60)

Sensitive level by Lactic acid test at T0 (baseline), T14d (after pre-treatment), T25d (10-day after self-recovery and product treatment start), T39d (14-day after product treatment) for all groups.

Instrument Assessment(N=60):

- **Corneometer:** skin hydration on both cheeks will be measured at T0 (baseline), T14d (after pre-treatment), T15d (Timm post-procedure), T16d (1-

day after self-recovery), T18d (3-day after self-recovery), T22d (7-day after self-recovery), T25d (10-day after self-recovery and product treatment start), T32d (7-day after product treatment), T39d (14-day after product treatment) for all groups.

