8.3. Efficacy Verification

8.3.1 Comparison between Time-points

A Shapiro-Wilk test will be used to test for normality of the baseline data (T0) and the change from baseline data (Tn-T0) at post-baseline time points at significance level alpha=0.01. When data passes normality (all normality of the distributions is confirmed for the same parameter), a parametric test will be used to test the null hypothesis that the mean change from baseline is zero. When data fails normality (if one or more normality of the distributions for the same parameter is rejected), a non-parametric test will be used.

Pre-treatment efficacy:

- a) T14d (after pre-treatment), T15d (Timm post-procedure) versus T0 (baseline)
- b) T16d (1-day after self-recovery), T18d (3-day after self-recovery), T22d (7-day after self-recovery), T25d (10-day after self-recovery) versus T15d (Timm post-procedure)

Post-treatment efficacy:

a) T32d (7-day after product treatment), T39d (14-day after product treatment) versus T25d (product treatment start)

The following will be calculated and reported for each evaluation parameter at applicable post-statistical baseline time point(s):

For self-assessment questionnaires, only the data of completing subjects will be analyzed. Questionnaire response options will be in the form of a 5-point semi-structured scale, ranging from one (1) to (5), where the score of one (1) will be the most negative/unfavorable rating and the score of five (5) will be the most positive/favorable rating the product can receive (the scale will also include a mid-point label "neither agree nor disagree"). Responses obtained for each question will be tested for normality using a Shapiro-Wilk test at significance level alpha=0.01, and if the data passes normality testing, mean scores will be used. Responses that are not normally distributed will be assessed using the median response. The percentage of ratings from

4 to 5 ("top XX box %") will be reported.

In the report appendices, raw data and open-ended questionnaire responses will be listed by subject. Data frequency and percentage will be presented for questionnaires and tolerability evaluations. Tolerability tables will also be sent to the Sponsor at the indicated interim data time points; SAQ data will be sent at study completion, for all completing subjects. Medians, means and percentage values will be reported to decimal place (0.0) for all questionnaire data.

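### The product-efficacy questionnaire is put to Group 1 only, so its top-box percentage can look favourable whether or not the serum works, and the design cannot tell which

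*Protocol*

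**What the plan says.** The synopsis, section 4 and section 5.6 of the protocol agree on who answers and when. Section 5.6 states "Self-Assessment Questionnaire on product efficacy will be answered by subjects at T14d (after pretreatment), T25d (10-day after self-recovery"), continuing "T32d (7-day after product treatment), T39d (14-day after product treatment) for Group 1 (N=30"). The cosmeticity questionnaire is also for Group 1 only. The one questionnaire put to both groups is post-procedure tolerance, which ends at "T22d (7-day after self-recovery), T25d (10-day after self-recovery) for all groups (N=60"). The study schedule in section 4 shows no self-assessment at T0.

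Section 8.3.1 describes a 5-point scale on which "the score of five (5) will be the most positive/favorable rating the product can receive". It gives a mean or median per question and adds that the percentage of ratings "4 to 5 ('top XX box %') will be reported". The analysis set is restricted: "For self-assessment questionnaires, only the data of completing subjects will be analyzed". No threshold and no comparator are given. The Group 1 versus Group 2 table in section 8.3.2 does not list this questionnaire.

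The Study Objective names two dimensions for evaluating the product: "the comparison of the effect before and after and the comparison with the control group".

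**The concern.** The result carries the label of product efficacy, yet its only input is how far women using the serum agree with favourable statements about their skin. Those women also use the standard cleanser and moisturiser morning and evening and the sunscreen in the morning (section 6.2). They also receive the laser, which section 5.5 says promotes dermal collagen, and saline and EGF during recovery. Group 2 receives all of these. A woman may agree that her skin feels hydrated because of the moisturiser alone.

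At stake is a headline percentage that could support a claim for the serum without containing information on the serum's effect. This is settled at data collection: no later analysis plan can compare Group 1 with answers that Group 2 was never asked to give.

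**Working it through.** **Step 1. Is there any reference for the percentage?**

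- *Control group:* none. Group 2 is not asked (synopsis, sections 4 and 5.6), although it attends T14d, T32d and T39d.
- *T0:* none. The first administration is T14d, after two weeks of serum.
- *T25d:* section 8.3.1 sets the post-treatment contrast as "T32d (7-day after product treatment), T39d (14-day after product treatment) versus T25d (product treatment start"). But Annex 11.3 uses a recovery form at day 10, whose items mostly credit prior product use, and a different post-treatment form afterwards. The items do not match.
- *T14d:* eleven of the twelve post-treatment items cover attributes also on the pre-treatment form, but T14d already follows serum use and precedes the laser, so it is not an untreated reference.

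**Step 2. What could the percentage look like with no serum effect?** The protocol states no figure to reproduce. Inputs:

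- n = 30 Group 1 completers (section 5.6).
- Background agreement p from the shared regimen: not in the protocol; assumed 40% to 80%.
- Count taken as favourable, c: not in the protocol; two assumptions. c = 15 means at least half. c = 21 is the smallest count with an exact one-sided p-value below 0.025 against 50% (0.0214; for 20 it is 0.0494).

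Formula: P(X ≥ c) = Σ (k = c to 30) C(30,k) p^k (1 − p)^(30 − k).

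Hand check at p = 0.5, c = 15: by symmetry, 0.5 + 0.5 × P(X = 15) = 0.5 + 0.5 × 0.1445 = 0.572.

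| Assumed p | P(X ≥ 15) | P(X ≥ 21) |
|---|---|---|
| 40% | 0.18 | not computed |
| 50% | 0.57 | 0.02 |
| 60% | 0.90 | 0.18 |
| 70% | 0.99 | 0.59 |
| 80% | >0.99 | 0.94 |

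The probability runs from near zero to near one, depending on two quantities that the protocol does not give and the design does not measure.

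**Step 3. Does an interval around the single-group figure help?** No. The exact 95% interval is 51% to 85% for 21/30 and 61% to 92% for 24/30. These describe precision about Group 1's own rate and say nothing about the rate without serum.

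**Step 4. What would a Group 2 reference give?** Take 30 per group, two-sided 5% and the normal approximation, with assumed rates (Group 2 versus Group 1). Power is 69% for 50% versus 80%, 39% for 60% versus 80%, and 49% for 70% versus 90%. For 60% versus 80%, the 95% half-width is 1.96 × √(0.6 × 0.4/30 + 0.8 × 0.2/30) = 1.96 × 0.115 ≈ 0.23. The difference would be interpretable but imprecise.

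**The case against.** Several points on the other side are fair.

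- *The objective is still served.* Its two dimensions are set for the study as a whole, not for each instrument. Clinical grading, instruments, imaging and the stinging test have T0 and both groups, and section 8.3.2 compares the groups on them. This stands. A reader might infer that the trial misses its own objective; the document does not support that.
- *No between-group claim is planned from this questionnaire.* True, and section 8.3.1 words it as a rating of the product. But the efficacy label remains, and it invites the reading that the data cannot bear.
- *The missing T0 is a weak complaint.* Largely true. Many items ask about change or about the product and make no sense before use. A T0 copy of the form would not repair the gap; the missing control answers are the main issue.
- *The shared regimen is not new at T0.* Both groups use it for 7 days beforehand (section 6.2), which may lower background agreement on change items. This bears on the assumed p, not on the lack of a reference.
- *Group 2 could not take the form as it stands.* Correct. The 14 English pre-treatment items do not name the product, but the form's Chinese heading refers to product use. In Chinese, the second item concerns tolerance during a procedure that takes place only at T15d. Rewording is needed.
- *The remedy is imperfect.* Group 2 receives no placebo, so expectation bias stays, and 30 per group gives wide intervals. Both are real limits and should be stated with the result.

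**Conclusion.** The point holds in a limited form. The questionnaire labelled product efficacy has no usable reference, so its top-box percentage can come out favourable with or without a serum effect, and nothing collected distinguishes the two cases.

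A reader might go further and infer that the percentage will come out favourable even for an inert serum. The document does not support that. It gives neither a background rate nor a definition of favourable, and under the assumptions above the probability is 0.18 at 40% agreement with the 15/30 cut-off and 0.02 at 50% with the 21/30 cut-off. The conclusion that the figure cannot be attributed to the serum needs neither assumption; only the illustrated probabilities do.

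Severity is minor to moderate: this is one outcome among many, and the clinical, instrumental, imaging and stinging outcomes already have T0 and Group 2.

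**What to change.** - **Collection (synopsis, section 4, section 5.6, Annex 11.3):** have Group 2 also answer the skin-state items at T14d, T32d and T39d. For both groups, make the product-use heading neutral, remove the lead-in that ties post-treatment items to product use, and leave out the procedure-tolerance item at T14d.
- **Reporting (section 8.3):** give the Group 1 minus Group 2 difference in top-box percentage with a 95% confidence interval, as descriptive.
- **Labelling:** call every item about the product itself (the T25d recovery items, recommendation and cosmeticity) consumer perception and not efficacy evidence. If Group 2 is not asked, apply that label to the whole questionnaire.
- **Reconcile in passing:** Annex 11.3 states a 5-point scale but prints Yes, No and Comments columns, from which a 4-to-5 percentage cannot be computed.

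The cost is a few minutes for Group 2 at visits already scheduled, plus wording changes. The downside is a difference that is imprecise with 30 per group and open to expectation bias because there is no placebo; the report should say so. Relabelling alone costs almost nothing.

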6.1. Test Products

Product No.	Formula#	Product Name	Label As
		Investigational F	roducts
			上海复硕正态- 电话:[name] 测试编号 C210579
1	899467 14	Facial serum	测试精华 配方号: 899467 14 用于全脸 50ml/瓶 批号: 生产日期:
			室温保存 20-25°C 禁止入口入眼,如不慎入眼,请立即用大量清水冲 洗。仅供本测试使用,禁止销售,防止儿童接触。
			受试者编号: 产品瓶号:
		Support Prod	lucts
2	730457 36	Standard cleanser	上海复硕正态-电话:[name] 测试编号 C210579 标准洁面 配方号: 730457 36 用于全脸 其他请看使用说明 125ml/瓶 批号: 生产日期: 室温保存 20-25℃ 禁止入口入眼,如不慎入眼,请立即用大量清水冲洗。仅供本测试使用,禁止销售,防止儿童接触。 受试者编号: 产品瓶号:
3	609801 04	Standard moisturization	上海复硕正态-电话:[name] 测试编号 C210579 标准面霜 配方号: 609801 04 用于全脸 其他请看使用说明 40ml/瓶 批号: 生产日期: 室温保存 20-25℃ 禁止入口入眼,如不慎入眼,请立即用大量清水冲洗。仅供本测试使用,禁止销售,防止儿童接触。 受试者编号: 产品瓶号:

Product No.	Formula#	Product Name	Label As
4	885218 3	Standard sunscreen	上海复硕正态-电话:[name] 测试编号 C210579 标准防晒霜 配方号: 885218 3 用于全脸 其他请看使用说明 40ml/瓶 批号: 生产日期: 室温保存 20-25℃ 禁止入口入眼,如不慎入眼,请立即用大量清水冲洗。仅供本测试使用,禁止销售,防止儿童接触。 受试者编号: 产品瓶号:
5	N/A	Complementary medicines EGF 重组皮肤生长因子	On marketed

6.2. Products Application and Usage Instruction

Mode of application

a. 1-week wash-out stage: T-7d ~ T0 for all groups

A.M.: Standard cleanser + Standard moisturizer + Standard SPF

P.M.: Standard cleanser + Standard moisturizer

b. 2-week pre-treatment stage: T0 ~ T14d

【Group 1-Facial Serum group】

A.M.: Standard cleanser + Test serum + Standard moisturizer + Standard Sunscreen

P.M.: Standard cleanser + Test serum + Standard moisturizer

Group 2-Non-treatment group

A.M.: Standard cleanser + Standard moisturizer + Standard Sunscreen

P.M.: Standard cleanser + Standard moisturizer

The standard sunscreen needs to apply to face every morning 15 minutes before sun exposure and re-apply if necessary. Keep out of eyes. No any other skin care or facial make up products are used.

c. 10 days recovery stage: T15d ~ T24d for all groups

A.M.: Sterile saline solution + EGF

P.M.: Sterile saline solution

d. 2-week post-treatment stage: T25d ~ T39d

【Group 1-Facial Serum group】

A.M.: Standard cleanser + Test serum + Standard moisturizer + Standard Sunscreen

P.M.: Standard cleanser + Test serum + Standard moisturizer

Group 2-Non-treatment group

A.M.: Standard cleanser + Standard moisturizer + Standard Sunscreen

P.M.: Standard cleanser + Standard moisturizer

The standard sunscreen needs to apply to face every morning 15 minutes before sun exposure and re-apply if necessary. Keep out of eyes. No any other skin care or facial make up products are used.

7. Procedure

7.1. Screening

Participation of the volunteers is purely voluntary. Before being entered into the study, the volunteers will be pre-screened by the investigator according to the criteria indicated in the selection of volunteers' section. Only subjects who meet the requirements of this section are eligible to participate in the study.

7.2. Conducting the Study

Pre-screening visit at T-7d

- a. Within 24 hours before screening visit, subjects will be asked not to use any cosmetic product on test areas.
- b. On the arrival, the subject will be informed about the nature of the study and the treatment procedure and a signed and dated informed consent form will be obtained. At the same time, one Photo release form will be also signed from each subject.
- c. A subject screening number will be automatically allocated (SC0X) by CRF.
- d. Demographic data collection.
- e. Medical examination, subject's interview on his medical history and concomitant medications.
- f. Subjects wash face with usual cleanser, then pat dry with clean tissue paper at center.
- g. Acclimatization to the room condition for 30 minutes (the conditions with a well-controlled room temperature (21 ± 1 °C) and humidity ($45\%\pm5\%$).
- h. Clinical assessment by will be done by dermatologist for screening.
- i. Verification of subject eligibility: inclusion/non-inclusion criteria and on-site clinical grading by Dermatologist.
- j. The weighted wash-out products and daily log will be delivered to each subject.
- k. Adverse Events/Local Intolerance will be checked and recorded.

Evaluation visit on T0: Baseline

- a. Subjects wash face with usual cleanser, then pat dry with clean tissue paper at center.
- b. Acclimatization to the room condition for 30 minutes (the conditions with a well-controlled room temperature (21 ± 1 °C) and humidity ($45\%\pm5\%$).
- c. Verification of inclusion/non-inclusion criteria for final eligibility.
- d. Clinical Assessment will be done by dermatologist for T0.
- e. VISIA 7 will be done by trained technician for T0.
- f. OCT scan will be done by trained technician for T0.
- g. Corneometer will be done by trained technician for T0.
- h. Vapometer will be done by trained technician for T0.
- i. Cutometer will be done by trained technician for T0.
- j. pH meter will be done by trained technician for T0.

- k. LA sting test will be done by trained technician for T0.
- The wash-out (standard) products will be weighted and returned to subjects; as the same time, the weighted
 investigational products and daily log will be delivered to each subject according to the randomization
 table.
- m. Adverse Events/Local Intolerance will be checked and recorded.

T0 to T14d

a. Subjects should apply the provided wash-out products twice a day at home, in the morning and in the evening.

Evaluation visit on T14d

- a. Subjects wash face with usual cleanser, then pat dry with clean tissue paper at center.
- b. Acclimatization to the room condition for 30 minutes (the conditions with a well-controlled room temperature (21 ± 1 °C) and humidity ($45\%\pm5\%$).
- c. Clinical Assessment will be done by dermatologist for T14d.
- d. VISIA 7 will be done by trained technician for T14d.
- e. OCT scan will be done by trained technician for T14d.
- f. Corneometer will be done by trained technician for T14d.
- g. Vapometer will be done by trained technician for T14d.
- h. Cutometer will be done by trained technician for T14d.
- i. pH meter will be done by trained technician for T14d.
- j. LA sting test will be done by trained technician for T14d.
- k. Self-assessment questionnaire will be answered by subjects for T14d.
- l. The investigational products and standard products will be weighted and returned to subjects, meanwhile, the daily log will be also checked.
- m. Adverse Events/Local Intolerance will be checked and recorded

Chemical Procedure visit and Timme evaluation on T15d

- a. Subjects wash face with usual cleanser, then pat dry with clean tissue paper at center.
- b. One questionnaire should be answered by subjects.
- c. Pre-process of xxx for procedure preparation.
- d. CO2-laser will be done by medical technologist.
- e. Clinical Assessment will be done by dermatologist for Timm post-procedure.
- f. VISIA 7 will be done by trained technician for Timm post-procedure
- g. OCT scan will be done by trained technician for Timm post-procedure
- h. Corneometer will be done by trained technician for Timm post-procedure
- i. Vapometer will be done by trained technician for Timm post-procedure
- j. Cutometer will be done by trained technician for Timm post-procedure
- k. pH meter will be done by trained technician for Timm post-procedure
- 1. Adverse Events/Local Intolerance will be checked and recorded.

Evaluation visit on T16d (1-day after self-recovery)

- a. Clinical Assessment will be done by dermatologist for T16d.
- b. VISIA 7 will be done by trained technician for T16d.
- c. OCT scan will be done by trained technician for T16d.

- d. Corneometer will be done by trained technician for T16d.
- e. Vapometer will be done by trained technician for T16d.
- f. Cutometer will be done by trained technician for T16d.
- g. pH meter will be done by trained technician for T16d.
- h. Self-assessment questionnaire will be answered by subjects for T16d.
- i. Adverse Events/Local Intolerance will be checked and recorded.

Evaluation visit on T18d (3-day after self-recovery)

- a. Clinical Assessment will be done by dermatologist for T18d.
- b. VISIA 7 will be done by trained technician for T18d.
- c. OCT scan will be done by trained technician for T18d.
- d. Corneometer will be done by trained technician for T18d.
- e. Vapometer will be done by trained technician for T18d.
- f. Cutometer will be done by trained technician for T18d.
- g. pH meter will be done by trained technician for T18d.
- h. Self-assessment questionnaire will be answered by subjects for T18d.
- i. Adverse Events/Local Intolerance will be checked and recorded.

Evaluation visit on T22d (7-day after self-recovery)

- a. Clinical Assessment will be done by dermatologist for T22d.
- b. VISIA 7 will be done by trained technician for T22d.
- c. OCT scan will be done by trained technician for T22d.
- d. Corneometer will be done by trained technician for T22d.
- e. Vapometer will be done by trained technician for T22d.
- f. Cutometer will be done by trained technician for T22d.
- g. pH meter will be done by trained technician for T22d.
- h. Self-assessment questionnaire will be answered by subjects for T22d.
- i. Adverse Events/Local Intolerance will be checked and recorded.

Evaluation visit on T25d (10-day after self-recovery and post-treatment started)

- a. Subjects wash face with usual cleanser, then pat dry with clean tissue paper at center.
- b. Acclimatization to the room condition for 30 minutes (the conditions with a well-controlled room temperature $(21\pm1 \, ^{\circ}\text{C})$ and humidity $(45\%\pm5 \, \%)$.
- c. Clinical Assessment will be done by dermatologist for T25d.
- d. VISIA 7 will be done by trained technician for T25d.
- e. OCT scan will be done by trained technician for T25d.
- f. Corneometer will be done by trained technician for T25d.
- g. Vapometer will be done by trained technician for T25d.
- h. Cutometer will be done by trained technician for T25d.
- i. pH meter will be done by trained technician for T25d.
- j. LA sting test will be done by trained technician for T25d.
- k. Self-assessment questionnaire will be answered by subjects for T25d.
- 1. The investigational products and standard products will be weighted and returned to subjects, meanwhile, the daily log will be also checked.
- m. Adverse Events/Local Intolerance will be checked and recorded.

Subjects will be pushed and required to answer one on-line questionnaire after the first application of test product at home.

Evaluation visit on T32d (7-day post-treatment started)

- a. Subjects wash face with usual cleanser, then pat dry with clean tissue paper at center.
- b. Acclimatization to the room condition for 30 minutes (the conditions with a well-controlled room temperature $(21\pm 1 \, ^{\circ}\text{C})$ and humidity $(45\% \pm 5 \, \%)$.
- c. Clinical Assessment will be done by dermatologist for T32d.
- d. VISIA 7 will be done by trained technician for T32d.
- e. OCT scan will be done by trained technician for T32d.
- f. Corneometer will be done by trained technician for T32d.
- g. Vapometer will be done by trained technician for T32d.
- h. Cutometer will be done by trained technician for T32d.
- i. pH meter will be done by trained technician for T32d.
- j. Self-assessment questionnaire will be answered by subjects for T32d.
- k. The investigational products and standard products will be weighted and returned to subjects, meanwhile, the daily log will be also checked.
- 1. Adverse Events/Local Intolerance will be checked and recorded.

Evaluation visit on T39d (14-day post-treatment started)

- a. Subjects wash face with usual cleanser, then pat dry with clean tissue paper at center.
- b. Acclimatization to the room condition for 30 minutes (the conditions with a well-controlled room temperature $(21\pm 1 \, ^{\circ}\text{C})$ and humidity $(45\% \pm 5 \, \%)$.
- c. Clinical Assessment will be done by dermatologist for T39d.
- d. VISIA 7 will be done by trained technician for T39d.
- e. OCT scan will be done by trained technician for T39d.
- f. Corneometer will be done by trained technician for T39d.
- g. Vapometer will be done by trained technician for T39d.
- h. Cutometer will be done by trained technician for T39d.
- i. pH meter will be done by trained technician for T39d.
- j. LA sting test will be done by trained technician for T39d.
- k. Self-assessment questionnaire will be answered by subjects for T39d.
- The investigational products and standard products will be weighted and returned; meanwhile, the daily log will be also checked.
- m. Adverse Events/Local Intolerance will be checked and recorded.

NB: all concomitant medications, AEs and local intolerances will be reported throughout the study.

8. Biostatistics and Data Management

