*Product Application		←	-						4		
*Tolerance feedback in dairy log		←	-						•		-
Distribute(D)/Return(R)/Weight(W) Investigational Product (IP) and Standard Product (STD)	X STD(D/W)	X STD/IP(D/W)	X STD/IP(R/W)						X STD/IP(D/W)	X STD/IP(W)	X STD/IP(R/W)
Compliance Check	X	X	X	X	X	X	X	X	X	X	X
AE/SAE Report	X	X	X	X	X	X	X	X	X	X	X
End of Study											X

All the measurements will be conducted under the conditions with a well-controlled room temperature (21 ± 1 °C) and humidity ($45\%\pm5\%$).

^{*}Double-arrow means the product continuous application for 2-week pre-treatment period and 2-week post-treatment;

5. Measurement

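### Section 7.2 conflicts with Section 6.2 and the schedule on product use, custody and cleanser, and its missing acclimatisation step mismatches two within-group comparisons (T15d v T0, T25d v T15d)

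*Protocol*

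**What the plan says.** **Home use, T0 to T14d.** Section 7.2 says: "Subjects should apply the provided wash-out products twice a day at home, in the morning and in the evening". Section 6.2, stage b, lists for Group 1: "A.M.: Standard cleanser + Test serum + Standard moisturizer + Standard Sunscreen", with serum again in the evening. The schedule footnote says: "Double-arrow means the product continuous application for 2-week pre-treatment period and 2-week post-treatment". At the T0 visit, Section 7.2 itself has the following: "investigational products and daily log will be delivered to each subject according to the randomization" table.

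**Custody from T14d.** Section 7.2 at T14d says: "The investigational products and standard products will be weighted and returned to subjects, meanwhile, the daily log will be also checked". The schedule marks return and weighing of investigational and standard products at T14d, and distribution and weighing at T25d. Section 6.2, stage c, lists for T15d to T24d, all groups, "A.M.: Sterile saline solution + EGF" in the morning and saline alone in the evening.

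**Cleanser at visits.** Section 7.2 at T0, T14d, T15d, T25d, T32d and T39d says: "Subjects wash face with usual cleanser, then pat dry with clean tissue paper at center". Inclusion criterion 13 limits subjects to supplied skin care products. Section 6.2 names a standard cleanser and rules out other skin care.

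**Acclimatisation.** Section 7.2 lists 30 minutes in the controlled room at T0, T14d, T25d, T32d and T39d (and at screening). T15d goes from the wash to the laser and then to the readings. T16d opens directly with "a. Clinical Assessment will be done by dermatologist for T16d", and T18d and T22d follow the same pattern. A note under the schedule fixes room temperature and humidity for all measurements but gives no dwell time.

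**The concern.** Sections 6.2 and 7.2 both describe what subjects do, and they differ. A site working from the visit-by-visit steps could give Group 1 an incomplete home-use instruction for the pre-treatment fortnight, which would shrink the randomised contrast at T14d and afterwards.

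Custody matters for a different reason. Section 8.3.1 places T16d, T18d, T22d and T25d v T15d under pre-treatment efficacy. If Group 1 has serum at home in that window and some women use it, its effect cannot be separated from that of the earlier pre-treatment. Only Group 1 would have it, so this would fall on the between-group comparison.

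The cleanser wording allows an uncontrolled product shortly before hydration, TEWL and pH readings. The acclimatisation gap means that some changes over time compare readings taken after different preparation. Comparison before and after is one of the two dimensions named in the study objective.

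**Working it through.** **1. Product conflicts, side by side.**

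| Point | Section 7.2 | Section 6.2, schedule or criteria |
|---|---|---|
| Home use T0–T14d | wash-out products, all subjects | 6.2 b: Group 1 adds serum twice daily |
| Products at T14d | weighed, given back to subjects | Schedule: returned at T14d, distributed at T25d |
| Cleanser at visits | usual cleanser | Criterion 13 and 6.2: supplied products only |

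Section 7.2 at T0 separates wash-out (standard) products from investigational products, so the T0–T14d line does not naturally cover serum. On custody, Section 7.2 says products go back to subjects at T14d, T25d and T32d, but says only that they are returned at T39d. It therefore distinguishes giving back from collecting. The schedule marks return at T14d and T39d, distribution at T25d, and weighing only at T32d. The two agree at T32d and T39d and disagree at T14d; at T25d the verb also differs.

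**2. Acclimatisation status of each Section 8.3.1 comparison.**

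| Comparison | Step listed at each visit | Matched? |
|---|---|---|
| T14d v T0 | yes / yes | yes |
| T15d v T0 | no / yes | **no** |
| T16d, T18d, T22d v T15d | no / no | yes |
| T25d v T15d | yes / no | **no** |
| T32d, T39d v T25d | yes / yes | yes |

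Two of eight comparisons are mismatched. The three early recovery comparisons match on acclimatisation, though T15d has a wash (before the laser) and T16d, T18d and T22d list none.

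**3. Group comparison.** Let the missing step shift a reading by b, equally in both groups. The group difference in change is (Δ1 + b) − (Δ2 + b) = Δ1 − Δ2. The shift cancels in expectation; extra measurement variance could still cost precision.

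**4. Size, illustration only.** The protocol gives at least 30 completers per group and a two-sided 5% level, but no effect size, SD or power. There is no power figure to reproduce.

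*Dilution.* Assume a standardised effect that gives 80% power at 30 per group: √(2/30) × (1.960 + 0.842) = 0.72. If a fraction f of Group 1 used no serum, the effect becomes 0.72 × (1 − f), and power ≈ Φ(2.80 × (1 − f) − 1.96):
- f = 10%: 71%
- f = 25%: 56%
- f = 50%: 29%

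*Preparation offset.* In a mismatched within-group test with n = 30, let the offset be b SDs of the change. The rejection rate under no true change is 1 − Φ(1.96 − b√30) + Φ(−1.96 − b√30):
- b = 0.1: 8.5%
- b = 0.2: about 20%
- b = 0.3: about 38%
- b = 0.5: about 78%

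Both f and b are assumptions. The protocol supports no particular value of either.

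**The case against.** The strongest reply is that Section 7.2, read whole, presupposes serum use. It delivers the investigational product at T0 by the randomisation table and weighs it at T14d, and the schedule marks a compliance check at every visit. Standard products belong to both groups' regimens, so the T0–T14d line is incomplete for Group 1 and does not forbid serum. This stands: a drafting carry-over is the likeliest explanation. A reader might infer that Group 1 would go without its pre-treatment because the site works from Section 7.2. The protocol does not support that, since nothing ranks Section 7.2 above Section 6.2.

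On custody, holding serum is not using it. Section 6.2, stage c, omits serum for all groups and no section tells anyone to apply it then. That also stands. What remains is a direct contradiction about who holds the product, in a window where use by one group would confound the comparison.

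On the cleanser, the sentence also appears at screening, before any product is supplied, and seems to have been carried forward. By T0 it could mean the supplied cleanser used for the past week. The wording is the same for both groups. This is the weakest of the three conflicts, and it still needs one clear word.

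On acclimatisation, a reader might infer that every recovery change, or the group comparison, is biased. The comparison table and the cancellation above show otherwise. The fixed room conditions help, but they do not replace a dwell time, and Section 5.3 itself makes the Corneometer reading depend on other variables being carefully controlled.

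**Conclusion.** The point holds in a limited form. Three statements in Section 7.2 conflict with Section 6.2, the schedule or the inclusion criteria and must be reconciled. Harm to the group contrast is conditional on the text being followed literally (home use) or on retained serum being used (custody). The protocol gives no basis for a probability or an effect size, so the power figures show sensitivity and are not an expected loss.

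The acclimatisation gap is certain as text and narrow in effect: it can bias T15d v T0 and T25d v T15d within groups, by an unknown amount. The conclusion that the group difference is unbiased in expectation assumes that the shift is the same in both groups. The point should be corrected because correction is cheap; it does not show that the trial's contrast is lost.

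**What to change.** Before first enrolment:

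1. Reconcile Section 7.2 with Section 6.2 and the schedule on home application from T0 to T14d, on custody of investigational and standard products from T14d to T25d, and on the cleanser used at visits. Which regimen is right is for the sponsor and the investigator; this review does not choose.
2. Apply one common preparation before instrument readings, with the same 30-minute acclimatisation in the controlled room, at all of T15d (after the laser, at one fixed time), T16d, T18d and T22d. State also what is done about washing at those visits. All eight Section 8.3.1 comparisons are then matched on acclimatisation. Adding the step at T16d, T18d and T22d alone would be worse: it would mismatch three comparisons that now match and leave T25d v T15d as it is.
3. If the T15d reading must be immediate, report T15d v T0 and all changes from T15d with that limitation.

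The cost is corrected procedure text and about 30 minutes at up to four visits, so at most 4 × 30 = 120 minutes per subject.
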